2.5.2 Statistical hypothesis, model, and method of analysis

The change from baseline in the GCCS of CogState test battery will be analyzed using a repeated measures analysis of covariance (ANCOVA) model in which treatment, age stratification factor, MMSE stratification factor, education level, APOE4 status (carrier vs. non-carrier), baseline cerebrovascular disease burden, visit (Weeks 26, 52, 78, 104, 130 and Week 156) and treatment-by-visit interaction are included as fixed-effect factors and baseline GCCS and visit-by-baseline GCCS interaction as covariates, with a common unstructured covariance matrix among visits between treatment groups. The adjusted mean changes at 3 years (Week 156) within each treatment, the difference in mean changes at 3 years (Week 156) between the two treatments, and its 95% confidence interval obtained from the above model will be presented. In addition, the treatment difference (LCZ696-valsartan) in mean changes from baseline to 3 years will also be expressed based on a standardized effect size (Cohen's d) with a 2-sided 95% confidence interval. The Cohen's d will be estimated by using the adjusted between-treatment mean difference, divided by the estimated pooled standard deviation. The estimated standard deviation for the mean difference is:

$$SD = \left(\frac{1}{n_1} + \frac{1}{n_2} \right)^{1/2} \hat{\sigma}$$

where n1 and n2 are the number of patients within each treatment group and $\hat{\sigma}$ is the pooled standard deviation of the within treatment group adjusted mean change. Cohen's d can be rewritten in terms of t value of the estimated between treatment group difference based on the adjusted mean changes from the model mentioned above:

$$t = \frac{\hat{\mu}_1 - \hat{\mu}_2}{SD} = \frac{\hat{\mu}_1 - \hat{\mu}_2}{\left(\frac{1}{n_1} + \frac{1}{n_2} \right)^{1/2} \hat{\sigma}}$$

$$\hat{d} = \frac{\hat{\mu}_1 - \hat{\mu}_2}{\hat{\sigma}} = \left(\frac{1}{n_1} + \frac{1}{n_2} \right)^{1/2} \times t$$

Confidence interval (CI) of Cohen's d is based on 95% CI of the noncentrality parameter of t value divided by the square root of the degrees of freedom from the estimated between treatment group adjusted mean change (Cumming and Finch 2001). The analysis is based on a direct likelihood method with an assumption of missing at random (MAR) for the missing data mechanism.

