2.5.5 Sensitivity analysis

The primary analysis methods are consistent under the assumption of ‘missing at random (MAR)’ for the missingness mechanism. Though this is deemed to be an appropriate choice for the primary analysis, this is an untestable assumption based on the observed data ([CHMP, 2010](#), [National Research Council, 2010](#)). Indeed it is conceivable that censoring, respectively the missing data mechanism (e.g., due to death) may be informative and that the cognitive function decline in patients who died would have been steeper than estimated under the MAR assumption. Thus, the primary analysis would favor the valsartan group in the presence of a reduction in mortality in the LCZ696 group. Alternatively, patients starting medications for treatment of AD or cognitive impairment may have had a steeper decline than estimated under the MAR assumption, if they would have not started the medication.

Due to this uncertainty on the missingness mechanism, the following sensitivity analyses will be performed to investigate the sensitivity of the primary analysis results to the MAR assumption.

Tipping point analysis

First, a tipping point analysis ([Permutt 2016](#)), which falls into the class of pattern mixture models, will be performed to evaluate the MAR assumption for missing data due to death, HF hospitalization and stroke.

This sensitivity analysis assumes that missing data due to death, HF hospitalization and stroke are missing not at random (MNAR). More specifically, it assumes that missing GCCS values due to death, HF hospitalization and stroke could have been worse than those imputed under the MAR assumption. It is implemented in the following steps:

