- for missing data due to withdrawal for unknown reasons, including on-treatment data only in the SAF
- for missing data due to censoring at the start of AD and cognitive impairment treatments, including all data in the FAS
- for missing data due to withdrawal for unknown reasons, including all data in the FAS

In a similar procedure, missing values due to respective reasons will be imputed assuming MNAR while assuming all other missingness mechanism to be MAR.

If model convergence issue arises in the tipping point analysis, the model in step 1 above will be modified by replacing the common unstructured covariance matrix with a compound symmetry covariance matrix between treatment groups. If convergence issue remains after implementing the compound symmetry covariance matrix, the model will be simplified by removing baseline cerebrovascular disease burden as explanatory factor from the model.

Joint model approach

To adjust for the non-ignorable missingness in the primary endpoint due to starting AD/CI related medication, a joint modeling of the primary longitudinal process and missingness mechanism will be performed using a shared parameter approach (Vonesh et al 2006). Specifically, a generalized linear mixed model (GLMM) for the longitudinal GCCS outcome and a Cox proportional hazard model for the time to starting AD/CI related medication will be fitted which share common unobserved patient-specific random effect. It is assumed that the longitudinal outcome process is independent of the time to starting AD/CI related medication conditional on the random effects.

Model for longitudinal outcomes

The repeated GCCS outcomes will be analyzed following a repeated measures ANCOVA model with treatment, age stratification factor, MMSE stratification factor, education level, baseline cerebrovascular disease burden, APOE4 status (carrier vs. non-carrier) are included as factors and baseline GCCS, assessment time (in days), assessment time by baseline GCCS and assessment time by treatment interaction as covariates having fixed effects. Further, a patient-specific random intercept and random slope (on time) is fitted to the model. In general, the model has the following mathematical form:

$$y_i(t) = m_i(t) + e_i(t)$$
$$m_i(t) = X_i^T(t)\beta + (b_{0i} + b_{1i}t)$$

where

$y_i(t)$ =GCCS outcome for i-th patient at time t (assessment time in months)

$m_i(t)$ = 'True' (unobserved) patient-specific mean GCCS outcome for i-th patient at time t

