$X_i(t)$ = Covariate vector having fixed effects on mean GCCS outcome for i-th patient (treatment, age stratification factor, MMSE stratification factor, education level, baseline

cerebrovascular disease burden, APOE4 status, baseline GCCS, assessment time, assessment time by baseline GCCS and assessment time by treatment)

β = Parameter vector representing fixed effects of covariate vector $X_i(t)$ on mean GCCS outcome at time t

b_{0i} =Patient-specific random intercept

b_{1i} =Patient-specific random slope on time

$e_i(t)$ = Measurement error,

Assumption:

- (b_{0i}, b_{1i}) 's are assumed to be following bivariate normal distribution with mean vector 0 and unstructured covariance matrix independently for all patients
- $e_i(t)$'s are assumed to be independently normally distributed with mean vector 0 and an covariance matrix with no correlation between the time points and an common variance σ_e^2 on the diagonal elements

Model for time to starting AD or CI related medication

Time to starting AD or CI related medication from randomization will be calculated as –

- Date of starting AD or CI related medication – Randomization date +1

Patients who do not start AD or CI related medication, their data will be censored at the earlier of –

- Last known date patient took study medication
- Date of withdrawal of consent
- Date of last visit

A exponential regression is fitted to the time to starting AD or CI related medication.

$$\lambda_i(t|H_i(t), X_i) = \lambda_0 \exp(X_i^T \gamma + \alpha m_i(t))$$

where

$\lambda_i(t|H_i(t), X_i)$ =Conditional intensity function at time t for i-th patient given the covariate and history of outcomes until time t, $H_i(t)$

λ_0 =Baseline hazard function that is constant over time

γ = Parameter vector representing fixed effects of time-independent covariate vector X_i on event risk (hazard) at time t

α =Fixed effect of ‘true’ patient-specific mean outcome at time t

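### The joint model for AD/CI medication start has no matching MAR fit, so a gap between its 3-year effect and the primary one cannot be attributed to informative censoring

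*SAP*

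**What the plan says.** SAP 2.5.2 (primary model): "visit (Weeks 26, 52, 78, 104, 130 and Week 156) and treatment-by-visit interaction are included as fixed-effect factors", together with visit-by-baseline GCCS and "with a common unstructured covariance matrix among visits between treatment groups". Each arm's mean is thus free at each visit, and the result is the Week 156 difference.

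SAP 2.5.5 opens by saying that "the following sensitivity analyses will be performed to investigate the sensitivity of the primary analysis results to the MAR assumption". Table 2-3 lists the joint model among the sensitivity analyses to the primary analysis.

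The longitudinal half of the joint model has "baseline GCCS, assessment time (in days), assessment time by baseline GCCS and assessment time by treatment interaction as covariates having fixed effects". It continues: "Further, a patient-specific random intercept and random slope (on time) is fitted to the model". The errors have a "covariance matrix with no correlation between the time points" and one common variance. There is no visit factor, polynomial or spline.

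The event half is an exponential regression for time to AD/CI medication. It is tied to the GCCS process through alpha, defined as "Fixed effect of ‘true’ patient-specific mean outcome at time t".

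The section plans no fit with alpha = 0 and none of the longitudinal half alone. It does not say how a 3-year treatment contrast is taken from the joint model. The fallback for non-convergence concerns only the form of the baseline intensity.

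**The concern.** A sensitivity analysis to MAR is informative when the missingness assumption changes and the rest stays fixed. Here the only planned MAR fit available for comparison is the primary repeated-measures model, and moving from that to the joint model changes three things:

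- the time form: free visit means become straight lines;
- the covariance: unstructured becomes random intercept and slope with independent errors;
- the missingness model: alpha is added.

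If the two 3-year effects differ, the report cannot say which change caused it. If they agree, offsetting shifts are possible. The estimate of alpha shows whether underlying GCCS is associated with starting AD/CI medication. It does not show how far the Week 156 treatment effect moves as a result.

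The direction matters as well. Protocol 1.1 describes a theoretical harm from reduced amyloid clearance over a prolonged period. A difference that emerges late is one shape compatible with that, and it is a shape that a straight line understates at Week 156.

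**Working it through.** **The plan's own figure.** The documents give no figure for the joint model. The nearest is SAP 3.1: 180 per group with 3-year data, at least 80% probability at d = 0.3, two-sided 5%.

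- n per group = 2 x (1.960 + 0.842)^2 / 0.3^2 = 175.
- Power at 180: 0.3 x sqrt(180/2) = 2.846; 2.846 - 1.960 = 0.886; normal probability 81.2%.
- SE of d at 180 per group is about sqrt(2/180) = 0.105.

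The stated figure reproduces.

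**Effect of the linear form with no informative censoring (alpha = 0).** The six visits are equally spaced; number them j = 1 to 6. With complete data, a random intercept and slope in the same time variable and independent errors, the generalised least squares line equals the ordinary least squares line, so no variance values are needed. The fitted value at Week 156 weights visit j by

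w_j = 1/6 + (j - 3.5)(6 - 3.5)/17.5 = -0.190, -0.048, 0.095, 0.238, 0.381, 0.524.

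Apply these to an assumed true treatment difference, scaled to 1 at Week 156:

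- Linear (j/6), or constant from Week 26: 1.00.
- Quadratic (j/6)^2: 0.91.
- Onset after Week 78 (0, 0, 0, 1/3, 2/3, 1): 0.079 + 0.254 + 0.524 = 0.86.
- Onset after Week 104 (0, 0, 0, 0, 1/2, 1): 0.190 + 0.524 = 0.71.
- Plateau by Week 52 (1/2, 1, 1, 1, 1, 1): 1.10.
- Plateau by Week 78 (1/3, 2/3, 1, 1, 1, 1): 1.14.

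A model with free visit means targets 1.00 in every case.

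**With 30% non-informative monotone dropout** (the loss assumed in SAP 3.3, spread evenly over the visits) and three assumed sets of variance components, the expected estimates become:

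| Shape | Share of true Week 156 effect |
|---|---|
| Linear or constant | 1.00 |
| Quadratic | 0.89 to 0.90 |
| Onset after Week 78 | 0.83 to 0.84 |
| Onset after Week 104 | 0.68 to 0.69 |
| Plateau by Week 52 | 1.11 to 1.12 |
| Plateau by Week 78 | 1.16 to 1.17 |

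On a true effect of 0.30, onset after Week 78 gives about 0.25 and plateau by Week 78 about 0.35.

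**Simulation.** 520 patients, 30% non-informative dropout, 60 replicates per shape, both models fitted by maximum likelihood, true effect 0.30. The linear-time estimate differed from the free-means estimate, in size of effect, by on average 0.00 (linear), -0.06 (onset after Week 78) and +0.04 (plateau by Week 78). In a single trial the two fits differed with an SD of about 0.04 even when the shape was linear.

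**Scale of the quantity being sought.** The documents give no AD/CI incidence. Suppose the arms differ by 1% to 5% in AD/CI starts and the unmodelled deficit is 0.5 to 1.0 SD. Informative censoring would then shift the effect by 0.01 x 0.5 = 0.005 to 0.05 x 1.0 = 0.05. The shift from the time form can equal or exceed this.

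**Limits.** Covariates were left out, and only post-baseline visits were used as responses. Table 2-3 also lists baseline among the joint model's time points; treating it as a response would change the percentages. I took the Week 156 contrast as treatment main effect plus slope times 156 weeks, because the SAP defines none.

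**The case against.** The case against giving this much weight is strong in several respects.

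- A reader might infer that this is the only check on informative AD/CI start. It is not. SAP 2.5.5 also plans tipping-point analyses for this censoring, in the safety set and in the FAS. They keep visit and treatment-by-visit terms, refit the primary model, and use penalties from 0 to 50%, so 0% is a built-in MAR anchor. The FAS supportive analysis uses data collected after AD/CI medication starts. This stands.
- A reader might infer that the trial's conclusion is at risk. SAP 2.5.2 rests the main conclusion on the primary model alone. Protocol 9.4.4 treats the joint model as something to explore and warns that it may fail or be hard to interpret if few patients start AD/CI medication. SAP 2.5.5 allows the results to be left out if it does not converge. This stands too.
- The percentages depend on shapes that I chose, and no passage predicts any of them. Protocol 3.2 describes decline in Alzheimer's disease as gradual, and a linear difference gives no shift. A shift of 0.05 is about half of the 0.105 SE. These points limit the size that can be claimed. They do not restore attribution, because the documents give no basis for assuming linearity either.
- A natural remedy would be to put the visit factor into the joint model. That is not clean: the hazard contains alpha times the patient's mean at time t, so the mean must be defined between visits. A visit factor needs an added interpolation rule and changes what enters the event part. Linear time is a defensible choice here.

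None of this answers the absence of an alpha = 0 fit.

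**Conclusion.** The point holds in a limited form. As planned, a difference between the joint-model and primary 3-year effects mixes time form, covariance and missingness, so it cannot be read as the effect of informative AD/CI start. Without any informative censoring, the time form alone contributes 0% if the treatment difference is linear in time (or constant from Week 26) and roughly -30% to +17% under the assumed late-onset and plateau shapes. Those figures rest on assumed shapes, assumed variances for the dropout case, the 30% loss figure and my definition of the contrast.

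The documents do not support reading this as a flaw in the primary analysis, as a gap with no other check, or as evidence that a late effect will in fact be masked. It is an inexpensive improvement to one sensitivity analysis.

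**What to change.** In SAP 2.5.5, Joint model approach:

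1. Fit the identical longitudinal submodel with alpha = 0 on the same data. The likelihood then separates, and this is an ordinary linear mixed model under MAR.
2. Define the Week 156 treatment contrast for both fits. State one time unit, since the section gives assessment time in days in one place and in months in another.
3. Report the change in that contrast between alpha = 0 and alpha estimated as the measure of sensitivity to informative AD/CI start. The gap between the alpha = 0 fit and the primary result then shows separately what the different mean and covariance structure contributes.

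Linear time need not be replaced by a visit factor. The cost is a few lines of SAP text and one extra fit that is simpler than the joint model. The limitation that remains is that the reported change is still conditional on the linear form.

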### 5.6.2 Discontinuation of study treatment

Discontinuation of study treatment occurs when study drug is stopped earlier than the protocol planned duration, and this can be initiated by either the patient or the investigator.

The investigator must discontinue study treatment for a given patient if he/she believes that continuation would negatively impact the risk/benefit of trial participation.

Study treatment must be discontinued under the following circumstances:

- Patient wish
- Pregnancy (see [Section 6.5.9](#) and [Section 7.7](#))
- Use of prohibited treatment as per recommendation in [Table 5-3](#)
- Any situation in which study participation might result in a safety risk to the patient

However; study treatment discontinuation does not constitute withdrawal from the study and should not lead to the patient being withdrawn from the study.

Every effort should be made to complete end of treatment (EOT) assessments within 3 months of the last study drug dose for patients who have discontinued study drug permanently. For patients who terminate the study early, they are expected, and should be encouraged, to attend all the protocol specified study visits and perform all measurements as stipulated in the visit schedule ([Table 6-1](#)) and remain in follow up for the duration of the trial.

If they fail to return for these assessments for unknown reasons, every effort should be made to contact them. If the patient cannot or is unwilling to attend any visit(s), the site staff should maintain regular telephone contact with the patient, or with a person pre-designated by the patient. This telephone contact should preferably be done according to the study visit schedule.

The investigator must contact the IRT to register the patient's discontinuation from study treatment and must determine the primary reason for the patient's premature discontinuation of study treatment and record this information on the Dosage Administration eCRF.

The emergence of the following circumstances will require permanent study drug discontinuation:

- Withdrawal of informed consent
- Investigator thinks that continuation would be detrimental to the patient's well-being
- Suspected occurrence of angioedema. A patient with any signs or symptoms of clinically significant angioedema should be thoroughly evaluated by the investigator

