### **6 Visit schedule and assessments**

Table 6-1 lists all of the assessments and indicates with an "x" when the visits are performed.

Patients/subjects must be seen for all visits on the designated day, or as close to it as possible. Missed or rescheduled visits should not lead to automatic discontinuation.

[figure not shown]
After randomization, study drug discontinuation (permanent or temporary) for any reason does not constitute withdrawal from the study and should not lead to the patient being withdrawn from the study. Patients who discontinue study drug should be requested to return for an End of Treatment visit (EOT) in which all of the assessments outlined in Table 6-1 will be performed.

Patients who prematurely discontinue the study for any reason should be scheduled for a visit as soon as possible, at which time all of the assessments listed for the end of study visit will be performed. At the end of study visit, all dispensed investigational product should be reconciled and the adverse event and concomitant medications reconciled on the CRF.

Every effort should be made to complete end of treatment (EOT) assessments within 3 months of the last study drug dose for patients who have discontinued study drug permanently. Patients who terminate study drug early are expected, and should be encouraged to, attend all the remaining protocol specified study visits and perform all measurements as stipulated in the visit schedule (Table 6-1).

For EOT / End of Study (EOS) visit, the PET and MRI scans will only be performed if prior scans were performed more than twelve months ago. The CCB, [REDACTED] FAQ, [REDACTED] assessments will only be performed if prior assessments were performed more than three months ago.

Documentation of attempts to contact the patient should be recorded in the source documentation.

After identifying a potential patient, an informed consent form (ICF) must be signed by the patient before performing all study-related screening. The AE and serious adverse event (SAE) reporting period begins at the time the ICF is signed.

A Visit 199 (end of run-in visit) will be completed for all patients who enter the treatment run-in epoch. For patients who discontinue during the treatment run-in epoch or who are not able to be randomized due to safety reasons, Visit 199 will be their discontinuation visit.

For patients that will be randomized, Visit 199 will be their end of treatment run-in disposition visit.

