2.5.3 Handling of missing values/censoring/discontinuations

The repeated measure ANCOVA modeling as described in the previous section is based on a direct likelihood method with an assumption of missing at random for the missing data mechanism. That means, missing data, including those from dropouts, will be implicitly predicted based on similar patients. By similar we mean patients with similar baseline covariates, measurement histories and who were randomized to the same treatment arm. Various analyses to assess the sensitivity of the primary analysis results to the MAR assumption are described in [section 2.5.5](#).

Data collected more than three months after patients permanent discontinuation of the study medication will be excluded from analyses in both the Safety and PPS analyses. In addition, data collected after patients starting treatments for AD or cognitive impairment will be excluded from “on-treatment” analyses.

Patients with no post-baseline assessments available will be excluded from the primary analysis. However, these patients will contribute to the imputation model for the missing GCCS scores in the sensitivity analyses.

Table 2-3 Overview of missing data handling in analyses for primary endpoint

Analysis	Analysis Set	Data excluded	Missingness assumption	Analysis method	Time points included	Imputed dataset required?
Estimand: The treatment effect had all patients stayed ‘on-treatment’ for the 3-year planned follow-up duration (Under ‘as-treated’ principle)						
Primary	SAF	Off-treatment (>3 months after last dose) After start of treatment for AD or cognitive impairment	MAR	Repeated measure ANCOVA	Weeks 26, 52, 78, 104, 130 and Week 156	No
Sensitivity to Primary analysis	SAF	Off-treatment (>3 months after last dose) After start of treatment for AD or cognitive impairment	MNAR for missing data due to death, HF hosp., stroke	Tipping point analysis followed by ANCOVA	Baseline, Weeks 26, 52, 78, 104, 130 and Week 156	Yes

	SAF	Off-treatment (>3 months after last dose) After start of treatment for AD or cognitive impairment	MNAR for missing data after starting treatments for AD or cognitive impairment	Tipping point analysis followed by ANCOVA	Baseline, Weeks 26, 52, 78, 104, 130 and Week 156	Yes

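### SAP 2.5.5 joint model: AD/CI drug starts count as events at any time after randomisation, but patients without a start are censored at last study drug, so the event rate is overstated (low severity; wrong as written)

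*SAP*

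**What the plan says.** SAP Section 2.5.5 (Joint model approach) links the longitudinal GCCS model to a model for time to starting AD/CI medication. The event time is "Date of starting AD or CI related medication – Randomization date +1", with no requirement that the start falls on treatment or near it. The censoring sentence covers non-starters only: "Patients who do not start AD or CI related medication, their data will be censored at the earlier of" three dates, the first of which is "Last known date patient took study medication"; the others are withdrawal of consent and last visit. The event model is simple: "A exponential regression is fitted to the time to starting AD or CI related medication", with a "Baseline hazard function that is constant over time".

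Two other parts of the plan bear on this.

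- **Follow-up after stopping drug.** Protocol Section 6 says: "Patients who terminate study drug early are expected, and should be encouraged to, attend all the remaining protocol specified study visits". Protocol Section 5.6.2 also expects patients to attend the visits "and remain in follow up for the duration of the trial". SAP Section 2.4.2 tabulates new AD/CI drug use over the whole post-randomisation phase.
- **The GCCS data window.** SAP Section 2.5.3 says: "Data collected more than three months after patients permanent discontinuation of the study medication will be excluded from analyses" in the Safety set and per-protocol set. The joint-model row of Table 2-3 carries the same exclusion.

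**The concern.** For a patient who stops drug but stays in the trial, the earliest of the three censoring dates is normally the last dose. Take a patient who stops at month 12. If AD/CI medication starts at month 30, the patient is an event with 30 months at risk. If it never starts, the same patient contributes 12 months. Whether the 18 or more months off drug count depends on the outcome. An exponential likelihood needs a risk window that does not depend on whether the event later happens.

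The rule also departs from the model's purpose, which is to adjust for GCCS values lost because AD/CI treatment began. A start more than 3 months after last dose loses no GCCS value in this analysis, because those values are already excluded as off-treatment. It still counts as an event and feeds the parameter that links the hazard to GCCS.

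At stake are the estimated hazard, possibly the treatment effect on that hazard, and through the shared random effects the joint model's GCCS result.

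**Working it through.** **Inputs from the documents.** The event and censoring rules and the constant baseline hazard are in SAP 2.5.5. Planned follow-up is 3 years. SAP 3.3 assumes 30% drop-out; this is a composite that includes death and loss to follow-up as well as drug discontinuation. Protocol 3.2 cites an earlier heart failure trial with more than a third off drug by 3 years. No AD/CI start rate is given, so the plan has no figure here to reproduce.

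**Assumptions.** Constant start rate λ, 1% to 4% per year (2% shown). A fraction p of patients stops drug, evenly spread over 3 years and independent of AD/CI start. First case: all stoppers are followed to 3 years. The link to GCCS is left out, so the exponential estimate is events divided by person-time.

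**Formulas, per patient.**

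- Events: 1 − e^(−3λ) = 1 − e^(−0.06) = 0.0582.
- Time from patients with an event: (1 − e^(−3λ))/λ − 3e^(−3λ) = 2.9118 − 2.8253 = 0.0865 years.
- Mean time to last dose: 3 − 1.5p.
- Person-time under the SAP rule: 0.0865 + 0.9418 × (3 − 1.5p).
- Person-time if non-starters are followed to 3 years: 0.0865 + 0.9418 × 3 = 2.912. This gives 0.0582/2.912 = 0.0200, the true rate.

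| p | Mean time to last dose (y) | Person-time, SAP rule (y) | Estimated rate | Estimated / true |
|---|---|---|---|---|
| 20% | 2.70 | 2.629 | 0.0222 | 1.11 |
| 30% | 2.55 | 2.488 | 0.0234 | 1.17 |
| 40% | 2.40 | 2.347 | 0.0248 | 1.24 |

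The ratios hardly change between 1% and 4% per year. Simulation agrees, and shows that about 8% to 17% of counted events fall more than 3 months after last dose.

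**Other assumptions (20%, 30%, 40% stopping).**

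- Exponential instead of uniform stopping, all followed: 1.11, 1.19, 1.27.
- Half of stoppers followed: about 1.05, 1.08, 1.12 (uniform) or 1.06, 1.10, 1.14 (exponential).
- No stoppers followed: 1.00.
- Events limited to last dose + 3 months, censoring still at last dose: 1.01 to 1.04.

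**Treatment hazard ratio, true value 1, all followed.** With 25% vs 35% stopping, mean times to last dose are 2.625 and 2.475 years, person-times are 2.559 and 2.417, and rates are 0.0228 and 0.0241. The apparent ratio is 1.06, against the arm that stops more. With 20% vs 40% it is 0.0248/0.0222 = 1.12. With equal stopping it is 1.00.

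**After the fix.** With one window ending at last dose + 3 months for starters and non-starters alike, the ratio is 1.00 to within simulation error in every cell.

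**The case against.** The strongest reply is that the hazard is a nuisance parameter. The model exists to adjust the GCCS comparison, and apart from a by-arm summary of AD/CI drug use in SAP 2.4.2, no conclusion is planned from AD/CI starts. A simulation of the shared-parameter model compared the two rules. It used 60 trials per scenario, 260 patients per arm, an assumed hazard link of −1, all stoppers followed and no true effect. The mean shift in the 3-year GCCS difference was −0.0004 with 30% stopping in both arms, and −0.0016 to −0.0025 with 20% vs 40%. The SD of the estimate was about 0.05, so the shift was 1% to 5% of one SD. This simulation was run once and did not cover stronger links or a start rate that rises after stopping. It is the only evidence on the GCCS effect, and it points to a small one.

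The hazard-ratio bias is also small against its noise. Ratios of 1.06 and 1.12 are 0.06 and 0.11 on the log scale; the simulated SD was 0.33 at 2% per year and 0.23 at 4%. Full follow-up of stoppers is an upper case, since some of the planned 30% drop-out is death or loss to follow-up. Table 2-3 might be read as limiting event times too, though it does not say so, and censoring at last dose would still not match a 3-month window.

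Three stronger readings are tempting, and the documents do not support them:

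- **The primary result is biased.** The primary repeated measures ANCOVA does not use this time variable.
- **AD/CI starts are otherwise unchecked.** Tipping-point analyses address them in both the Safety set and the FAS, and the supportive FAS analysis keeps data after a start.
- **A false treatment effect on AD/CI starts will appear.** That needs different discontinuation by arm, which nothing in the plan predicts.

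The SAP also warns that this model may not converge and may be left out of the report. What remains is the mismatch itself, which no other section removes.

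**Conclusion.** The rule is wrong as written, and the severity is low. Person-time off drug is counted only for patients who later have the event. Under constant assumed start rates, with stopping spread evenly and independent of AD/CI start, the event rate is overstated by about 11% to 24% at 20% to 40% stopping with full follow-up. It is about half that if half of the stoppers are followed, and about 1% to 4% if event times are limited to 3 months after last dose. The treatment hazard ratio moves only if the arms stop at different rates. The damage is confined to the event part of one sensitivity model; the effect on its GCCS treatment difference is probably small but is not settled. Confidence is high in the mismatch and much lower in any practical consequence.

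**What to change.** In SAP 2.5.5, define one end of follow-up for every patient: the earliest of last study drug + 3 months, withdrawal of consent and last visit. Count an AD/CI start as an event only if it falls on or before that date; otherwise censor at that date. This matches the on-treatment window for GCCS.

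Counting all starts and censoring non-starters at last visit or withdrawal of consent would also remove the bias. It would keep events that remove no analysed GCCS data, so it fits the model's purpose less well.

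The cost is one sentence and one derived time variable. The downside is slightly fewer events, in a model where the SAP already allows for low incidence and failure to converge.
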